7.2.2.2. Dose Escalation Method

[Table JBDA 7.1.](#) outlines the proposed dose-escalation scheme. In this study, the escalation will start from the lowest planned dose, the maximum allowed dose increment is 100%, and each new dose level will have a minimum of 3 patients enrolled to it. The Bayesian model-based toxicity band method (Neuenschwander et al 2008) that incorporates prior expectations about the dose-toxicity curve will be fitted to the data at the end of each cohort to recommend a dose for the next cohort. The toxicity band method is a Bayesian model-based design with built-in escalation with overdose control mechanism. After each cohort, the toxicity band model will utilize data from all available cohorts to make dose recommendation, based on the model based posterior probability of a DLT at each dose, and the overdose control criteria. The toxicity band method will stop if the pre-specified maximum number of subjects is reached or the recommended next dose has been taken by 9 patients.

During the escalation, the investigators and Lilly CRP will consider both the model recommendation and the observed DLT rate at each cohort to determine the next dose level and determine when to stop the escalation. Dose levels for each cohort will not exceed those recommended by the toxicity band model. Dose escalation will take into account PK and PD information when available. Additional patients may therefore be enrolled at a specific dose level to characterize PK/PD.

Intermediate or higher dose levels will be explored if deemed necessary after discussion between the sponsor and investigators. The JBDA toxicity band model has the ability to accommodate additional dose levels naturally.

Details regarding the JBDA toxicity band design are provided in [Attachment 10](#).

Table JBDA 7.1. Proposed Dose Escalation Scheme

Dose level	LY3009120 Dose (given BID) (mg)	Predicted Median AUC _{0-τ,ss} (ng*h/mL)	Predicted 5th and 95th percentiles AUC _{0-τ,ss} (ng*h/mL)	Predicted Median C _{max,ss} (ng/mL)	Predicted 5th and 95th percentiles C _{max,ss} (ng*h/mL)
1	50	1320	571-2560	139	63-250
2	100	2250	989-4550	232	108-442
3	200	2620	1150-5050	272	125-499
4	300	2770	1220-5310	290	140-528
5	400	3230	1440-6250	339	160-618
6	500	3780	1670-7460	393	187-750
7	600	3840	1630-7690	407	182-773
8	700	3980	1770-7780	419	201-771

Abbreviation: AUC_{0-τ,ss} = area under the plasma concentration versus time curve from time 0 to the end of the dosing interval (where τ=12h); C_{max,ss} = maximum observed drug concentration during a dosing interval at steady state.

If, during dose escalation, a situation presents itself that is not described above, the investigator and Lilly CRP will determine the best method to select the appropriate dose for the patient(s) involved using all available information. This decision will be documented in writing. No dose escalations can occur without prior discussion and agreement between the site-specific investigator and the Lilly CRP. Written notification will be sent to the site specifying the dose to be used for each patient at each dose level.

The first patient enrolled in Part A of the study (Cohort 1) must complete 28 days of dosing before enrolling subsequent patients at that dose level. Once the first patient has completed 28 days of dosing without significant toxicity, the second and third patients may be enrolled concurrently. For cohort 2, the first patient must complete 15 days before enrolling subsequent patients. For cohorts 3 and beyond patients may be enrolled concurrently.

7.2.3. Dose Confirmation Phase

Once the MTD has been defined, the dose-confirmation phase will be opened. Enrollment will be expanded by approximately 45 additional evaluable patients with advanced unresectable/metastatic melanoma and NSCLC. The dose(s) to be studied in Part B will be defined at the end of dose escalation after a safety, PK, and PD review. These dose(s) will not exceed the MTD.

If DLT-equivalent toxicities in the first cycle (that is, toxicities that would meet the DLT criteria in Section 7.2.2.1) occur in 33% or more of patients within this confirmation phase, then investigators and the Lilly CRP will assess the nature and severity of these toxicities. No additional patients will be accrued until this safety review is completed and a decision is made either to continue at the current dose or to de-escalate the dose and define a new dose for the confirmation portion. If DLT-equivalent toxicity occurs in one third or more of patients during

Cycles 1 or 2 of Part B (with a minimum of 6 patients enrolled), the enrollment of new patients will cease until the Lilly CRP or CRS and study investigators assess the severity and nature of the toxicity.

The safety review and decision will be documented in writing.

7.2.4. Dose Adjustments and Delays

7.2.4.1. Dose Adjustments within a Cycle

Part A: In the event that a patient experiences a DLT, DLT-equivalent or a Grade 3/4 toxicity that is not dose-limiting, treatment will be interrupted. Dosing can be resumed after resolution of the toxicity to baseline levels at the next lower dose level already deemed safe upon discussion with the Lilly CRP.

Part B: In the event that a patient experiences a DLT-equivalent toxicity that resolves with treatment interruption, at the investigator's discretion and with the agreement of the Lilly physician or their designate, treatment may be resumed at a lower dose level than the one that was associated with the DLT event.

Part A and Part B: In the event that a patient experiences visual symptoms, or an abnormality is detected during in-treatment eye/vision assessment, treatment will be interrupted and appropriate therapeutic measures will be taken. After resolution of symptoms to baseline and/or normalization of eye tests, dosing can resume at the next lower dose level already deemed safe, after discussion with the Lilly CRP.

7.2.4.2. Dose Adjustment between Cycles

Before the start of each cycle, hematological toxicity except anemia must resolve to baseline and all nonhematological toxicities must resolve to CTCAE v4.0 Grade 0, 1, or baseline (except alopecia and fatigue). The start of a cycle may be delayed up to 2 weeks to allow sufficient time for recovery. Patients who do not recover from toxicity within 2 weeks should be discontinued. If the patient has received granulocyte colony stimulating factors (G-CSFs) (see Section 7.5) and/or if the patient is in Cycle 3 or beyond and is continuing to receiving benefit from therapy, additional delays may be acceptable if agreed upon by both the investigator and sponsor.

The dose should be reduced to the previous dose level for the next cycle of therapy if a patient had at least 1 of the following events or if the investigator thinks it is in the best interest of the patient:

- A DLT-equivalent toxicity (Part A patients in Cohort 2 and above; all patients enrolled in Part B)
- Omission of more than 25% of doses in a single cycle due to toxicity (Part B only).

If a patient experiences a DLT-equivalent toxicity at the reduced dose, then he/she will be discontinued from treatment. If the patient requires a dose reduction or omission in the absence of significant toxicity, then he/she may continue with treatment if the investigator determines that he/she is receiving benefit. Re-escalation to the original dose is acceptable in the absence of

continuing toxicity, provided that this dose is not greater than the declared MTD. If subsequent dose reduction is again required, the patient must be maintained at the reduced dose level for all remaining cycles. If a patient in the first cohort experiences a DLT in the first cycle of treatment, he/she will be discontinued from the study.

7.3. Method of Assignment to Treatment

Patients who meet all criteria for enrollment will be assigned to receive LY3009120 in this study. Before each patient's enrollment into the study, an eligibility check must be conducted between the investigational site and the Lilly clinical research personnel to confirm that each patient meets all enrollment criteria. Upon confirmation of eligibility, the sponsor will confirm the dose, cohort, and identification number assignment for each patient. No dose escalations (that is, to the next cohort) can occur without prior discussion and agreement with the responsible Lilly CRP.

If investigators have eligible patients who have consented concurrently, up to 6 patients may be entered at a particular dose level provided that accrual has not ceased due to excessive toxicity. This enrollment procedure is allowed because of the advanced disease state of this patient population and the screening involved in defining eligibility. This event should be approved by the sponsor following discussions with the investigators.

7.4. Blinding

This is an open-label study.

7.5. Concomitant Therapy

No other chemotherapy, radiotherapy, immunotherapy, cancer-related hormone therapy, or experimental drugs will be permitted while the patients are on this study. An exception will be made for prostate cancer patients continuing GnRH agonist therapy or breast cancer patients continuing antiestrogen therapy (for example, an aromatase inhibitor). The need for any form of radiotherapy (including palliative) will be cause for early discontinuation from the study. In addition, any disease progression requiring other forms of specific antitumor therapy will also necessitate early discontinuation from the study. Appropriate documentation for all forms of premedications, supportive care, and concomitant medications must be captured on the case report form.

Patients should receive full supportive care with the exception that the routine use of G-CSF is not permitted during this study. Patients should not receive G-CSF prophylactically in any cycle. In Part A, no G-CSF use will be allowed in Cycle 1 unless hematological DLT is declared. In Cycle 2 and above and in Part B, patients may receive G-CSF or granulocyte-macrophage colony-stimulating factor therapeutically for neutropenia or fever with neutropenia according to the most recent update of the American Society of Clinical Oncology (ASCO) guidelines for the use of white blood cell growth factors (Smith et al. 2006). During treatment with G-CSFs study drug administration will be discontinued. G-CSFs must be discontinued at least 24 hours before resuming treatment with study drug treatment (pegylated colony-stimulating factors should be discontinued at least 14 days before resuming therapy with study drug). If clinically indicated at

any time during the study, erythropoietin and packed red blood cell transfusions may be used according to ASCO guidelines (Rizzo et al. 2008).

Based on the available nonclinical data, there is a possible risk of clinical drug-drug interaction when LY3009120 is administered with agents that are metabolized by CYP3A4. In the absence of more data to refine the risk of interaction, caution is warranted in the concomitant use of LY3009120 with CYP3A4 substrates with a narrow therapeutic margin (for example, alfentanil, cyclosporine, diergotamine, ergotamine, fentanyl, pimozide, quinidine, sirolimus, and tacrolimus).

All concomitant medications should be recorded throughout the patient's participation in the study.

7.6. Treatment Compliance

Patient compliance with study drug will be assessed at each visit by direct questioning, patient's diary examination and counting returned capsules. Deviation(s) from the prescribed dosage regimen should be recorded on the case report form (CRF).

The patient must take $\geq 75\%$ of the intended doses to be deemed compliant with study drug administration. Similarly, a patient may be considered noncompliant if he or she is judged by the investigator to have intentionally or repeatedly taken more than the prescribed amount of medication. Potential discontinuation of a patient due to study drug noncompliance will be discussed between the investigator and the Lilly CRP before making the final determination for discontinuation.

7.6.1. Evaluable Patients

Patients who withdraw from the study before receiving study drug will be replaced and will not be included in the safety or efficacy assessments. Safety analyses will be conducted on all patients who have received at least 1 dose of study drug, regardless of whether they are deemed evaluable for the assessment of a dose level.

In Part A, patients who discontinue from the study before receiving at least 75% of planned doses of LY3009120 in Cycle 1 will be deemed non-evaluable for assessment of safety at that dose level and may be replaced unless they experience a DLT or dose omission/reduction due to toxicity prior to withdrawal.

Patients who receive at least 75% of the planned doses of LY3009120 but discontinue from study treatment before the end of Cycle 1 will be considered evaluable for the assessment of a dose level provided it can be documented whether the patient did or did not experience a DLT within 28 days of Day 1 in Cycle 1.

Part A: If the patient is noncompliant during Cycle 1 due to reasons other than drug-related toxicity he or she will be considered non-evaluable and may be replaced.

Part B: If the patient is noncompliant during Cycle 1 or Cycle 2 due to reasons other than drug-related toxicity or disease progression, he or she will be considered non-evaluable and may be replaced for the purpose of response assessment.

In Part A, nonevaluable patients may be replaced to ensure that no fewer than 3 patients receive at least 75% of planned doses of LY3009120 in Cycle 1 at each dose level, unless enrollment to that cohort has stopped due to DLT.

Patients who are not evaluable for pharmacokinetics, but who complete 1 cycle of therapy, may be replaced upon consultation with the investigator(s) and the Lilly CRP to ensure adequate PK data collection, unless enrollment to that cohort has stopped due to a DLT.

8. Safety, Pharmacokinetic, Pharmacodynamic, and Efficacy Data Collection

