7.2.2.1. Dose-Limiting Toxicity Determination and Maximum Tolerated Dose Definition

Dose-limiting toxicity (DLT) is defined as an adverse event (AE) during Cycle 1 for a patient enrolled in Part A that is possibly related to the study drug and fulfills any one of the following criterion using the National Cancer Institute's (NCI) Common Terminology Criteria for Adverse Events (CTCAE) v4.0:

- ≥CTCAE Grade 3 non-hematological toxicity. Exceptions will be made for:
 - Nausea, vomiting, diarrhea, or constipation that can be controlled with appropriate care. Grade 3 and Grade 4 nausea, vomiting, or diarrhea should be considered DLT if persisting more than 48 hours despite maximum supportive intervention.
 - Grade 3 elevations of ALT and/or AST lasting fewer than 8 days, without evidence of other hepatic injury, in the setting of preexisting hepatic metastasis and baseline elevation of these values, may not be considered a DLT if agreed by the study investigator and Lilly CRP.
 - Grade 3 rash that resolves or improves to a Grade 2 or less within 7 days and remains tolerable may not be considered a DLT if agreed by the study investigator and Lilly CRP/CRS.
- CTCAE Grade 4 hematological toxicity of >5 days duration.
- Grade 4 thrombocytopenia of any duration
- Grade 3 thrombocytopenia with bleeding
- Grade 3 febrile neutropenia
- Any other significant toxicity deemed by the primary investigator and Lilly clinical research personnel to be dose limiting (for example, any toxicity that is possibly related to the study medication that requires the withdrawal of the patient from the study during Cycle 1).

Investigators, together with the Lilly CRP, can declare a DLT if a patient is experiencing increasing toxicity during treatment, and it becomes clear that it is not going to be possible to complete the treatment without exposing the patient to excessive risk.

A DLT-equivalent toxicity is defined as an AE occurring between Day 1 and Day 28 of any cycle (other than Cycle 1) for a patient enrolled in Part A or in any cycle for a patient enrolled in Part B (including Cycle 1) that would have met the criteria for DLT if it had occurred during Cycle 1 for a patient enrolled in Part A.

For the purpose of this study, the MTD is defined as a safe dose that has the highest probability of DLT in the targeted toxicity interval (20 to 35%). A safe dose means that the probability of DLT larger than 35% is below 25%.

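### The two Part A evaluability rules in Protocol 7.6.1 disagree: the noncompliance rule lacks the DLT exception that the discontinuation rule has, so a real DLT can be set aside at dose-level assessment

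*Protocol*

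**What the plan says.** Protocol 7.6.1 (Evaluable Patients) has two rules for Part A patients who receive too little drug in Cycle 1.

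- **Discontinuation rule.** A patient who leaves the study before taking 75% of planned Cycle 1 doses is non-evaluable for that dose level and "may be replaced unless they experience a DLT or dose omission/reduction due to toxicity prior to withdrawal".
- **Noncompliance rule.** "If the patient is noncompliant during Cycle 1 due to reasons other than drug-related toxicity he or she will be considered non-evaluable". Replacement is then allowed, and no DLT exception follows.

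Protocol 7.6 sets the compliance threshold at 75% or more "of the intended doses to be deemed compliant with study drug administration". A patient may also be judged noncompliant for having "intentionally or repeatedly taken more than the prescribed amount of medication".

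The DLT definition in Protocol 7.2.2.1 does not depend on compliance: "Dose-limiting toxicity (DLT) is defined as an adverse event (AE) during Cycle 1 for a patient enrolled in Part A", subject to relatedness and the grade criteria. SAP 5.3.3 repeats the 75% threshold. SAP 5.2 defines no DLT-evaluable set. SAP 5.8.2 lists DLTs for all Part A patients on therapy.

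**The concern.** The qualifier in the noncompliance rule describes why doses were missed. It does not ask whether a DLT occurred. A patient can therefore miss doses through travel or forgetting, have a DLT later in Cycle 1, stay on study and be classed as non-evaluable by mandatory wording. The parallel rule a few lines earlier carries the exception, so its absence here looks like an oversight.

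The primary objective is a recommended Phase 2 dose that can be given safely, and cohorts may have only three patients. If the escalation count follows the evaluability rule, one observed DLT is replaced by a new patient, and the model sees a cleaner cohort than the one treated. Two teams could also feed the model different counts from the same data, because the documents do not define its input set.

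**Working it through.** **1. The two rules applied to the same patient.** The patient has under 75% of Cycle 1 doses, missed for unrelated reasons, and a DLT.

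| Patient | Discontinuation rule | Noncompliance rule |
|---|---|---|
| Stays on study | does not apply | non-evaluable, replaceable |
| Discontinues before 75% | stays evaluable (DLT exception) | non-evaluable, replaceable |

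The first row is a clean exclusion and the second a contradiction. Nothing else in the protocol or SAP says that a DLT overrides the noncompliance rule.

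**2. How much must be missed.** Twice-daily dosing for 28 days, less the omitted Day 1 evening dose in Part A (Protocol 7.2.1), gives 2 × 28 − 1 = 55 doses. Since 0.75 × 55 = 41.25, a patient is below threshold after missing 14 doses (41/55 = 74.5%), about a week of dosing.

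**3. Check of the model setup.** Inputs are from Attachment 10: logit p(d) = α + β log(d/700), with (α, log β) bivariate normal, mean (−0.092, 0.359), SD (2.507, 0.907), correlation 0.282. A dose is excluded if P(p(d) > 0.35) exceeds 0.25. Among the remaining doses, the one with the highest probability of lying in the 0.20 to 0.35 band is recommended.

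Table 1 of the attachment follows from logit(m) = logit(0.005) × log(d/700)/log(50/700). At 300 mg this is −5.293 × (−0.847)/(−2.639) = −1.70, so m = 0.155. All eight doses reproduce to three decimals: 0.005, 0.020, 0.075, 0.155, 0.246, 0.337, 0.423, 0.500.

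**4. Effect of one reclassified patient.** The posterior was computed on a grid, assuming 0/3 DLTs at every lower level. Three counts at the current dose are compared:

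- 0/3: the DLT patient is set aside and replaced, and the three counted patients have no DLT.
- 1/3: the DLT patient is counted in a cohort of three.
- 1/4: the DLT patient is counted alongside the same three DLT-free patients.

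The entries are P(p > 0.35) at the next listed dose; above 0.25 that dose is excluded.

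| Current → next dose (mg BID) | 0/3 | 1/3 | 1/4 |
|---|---|---|---|
| 50 → 100 | 0.039 | 0.453 | 0.355 |
| 100 → 200 | 0.053 | 0.397 | 0.334 |
| 200 → 300 | 0.054 | 0.358 | 0.294 |
| 300 → 400 | 0.055 | 0.327 | 0.266 |
| 400 → 500 | 0.058 | 0.312 | 0.254 |
| 500 → 600 | 0.061 | 0.306 | 0.248 |
| 600 → 700 | 0.055 | 0.291 | 0.232 |

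The third decimal depends slightly on the grid (by up to about 0.003 at 700 mg); no decision changes.

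- With 0/3 the next dose is permitted at every level, and each of these steps is within the 100% increment cap.
- With 1/3 the next dose is excluded at every level. At 50 mg the current dose also fails (0.259), so no dose is admissible.
- With 1/4 the next dose is excluded from 50 to 400 mg. At 500 and 600 mg it passes and is recommended. The change between 400 and 500 mg rests on 0.254 against 0.248, close to the 0.25 limit.

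**5. How often.** The documents give no noncompliance rate, so q is assumed to be 5% to 20%, independent of DLT. With true DLT rate p, the chance of at least one such patient among three is 1 − (1 − pq)³.

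- p = 0.25, q = 0.05: 1 − 0.9875³ = 3.7%
- p = 0.35, q = 0.20: 1 − 0.93³ = 19.6%
- p = 0.05, q = 0.05: 1 − 0.9975³ = 0.7%
- p = 0.10, q = 0.20: 1 − 0.98³ = 5.9%

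**The case against.** **The exclusion from the model is inferred.** A reader might conclude that the protocol removes such DLTs from the escalation count. It does not say so. Protocol 7.2.2.2 has the model use data from all available cohorts, without mentioning evaluability. This stands. What remains is that 7.6.1 separates safety analysis of all treated patients from evaluability for assessing a dose level, so exclusion from the dose-level count is the ordinary reading of non-evaluable.

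**Decision-makers would still see the event.** Adverse events are the primary escalation criterion (Protocol 7.2.2). The observed DLT rate is weighed with the model, whose recommendation is an upper limit. Safety is reviewed before each escalation (10.9). Replacement is optional. These safeguards are real, but they leave it to judgement to undo a rule written as mandatory.

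**The case is narrow.** After a DLT, dosing stops: "In the event that a patient experiences a DLT, DLT-equivalent or a Grade 3/4 toxicity that is not dose-limiting, treatment will be interrupted". Doses missed because of the DLT are therefore toxicity-related and outside the rule. In the first cohort, a Cycle 1 DLT leads to discontinuation from the study (7.2.4.2), so a patient then below 75% also falls under the rule with the exception. The 50 mg case is a conflict between rules, not a clean exclusion.

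**Three stronger readings are not supported.**

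- That the error always lowers the DLT rate: a replacement patient may also have a DLT.
- That the set-aside DLT is the strongest toxicity evidence: only possible relatedness is required, intercurrent illness can confound attribution, and after over-intake the DLT reflects more than the assigned dose.
- That the model could jump to its unrestricted recommendation: after 0/3 at 200 mg that is 500 mg, a 150% increase, which the 100% cap bars.

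**Conclusion.** The concern holds as an inconsistency between two evaluability rules, combined with an undefined model input set. Taken literally, the noncompliance rule can set aside a real DLT when a dose level is assessed, and no other provision repairs it. It does not remove the event from safety reporting, and the documents do not establish that it removes the event from the model.

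The case is uncommon: about 4% to 20% per three-patient cohort for true DLT rates of 25% to 35%, and about 0.7% to 6% for rates of 5% to 10%, both under the assumed 5% to 20% noncompliance. When it occurs and the count follows evaluability, one patient can turn a hold into an escalation: at every level from 50 to 600 mg BID if the alternative count is 1/3, and at 50 to 400 mg if it is 1/4. These results assume 0/3 at all lower levels and a DLT-free replacement.

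**What to change.** Reconcile the two paragraphs of Protocol 7.6.1. Limit the Part A noncompliance rule to patients who have not had a DLT, so that a patient with a DLT after taking no more than the assigned dose stays evaluable whether or not the patient discontinues. List DLTs that follow intake above the prescribed amount separately, with the actual dose taken.

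State in the SAP, in 5.2 or 5.3.2, that this is the set of patients entering the toxicity band model. The DLT listing in SAP 5.8.2 already covers all Part A patients on therapy and needs no change.

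The cost is one sentence in each document. No patients are added, and no dose or treatment rule changes.
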